This 3.5 year project will be a randomized controlled trial testing a combined, integrated behavioral approach to management in older Veterans (aged ≥ 50 years) who are diagnosed with OSA, are prescribed PAP therapy, and also meet diagnostic criteria for insomnia. This novel intervention will combine essential elements of a CBT-I intervention (for insomnia) plus a behavioral intervention to improve PAP adherence. The combined, integrated intervention will be provided using allied health personnel compared to an active control condition (consisting of a general sleep and PAP education program) among older Veterans (N=120 total participants, 60 per group). Structured outcome assessments will be collected at baseline, post-treatment (i.e., after completion of the intervention or control condition), and at 3- and 6-months follow-up. A brief telephone interview will be conducted at 12-month follow-up. Outcomes assessed will include subjective (i.e., questionnaire, sleep diaries) and objective (i.e., wrist actigraphy) measures of sleep, objective measures of PAP adherence (downloaded from PAP equipment), mood and other measures of health-related quality of life. Data will also be collected at post-treatment, and at 3- and 6-months follow-up to assess beliefs and attitudes about sleep and OSA. Adherence with key aspects of the intervention will be collected in intervention participants during the treatment phase, and intervention participants will be invited to participate in focus groups after completing their 6-month follow-up to identify factors that act as facilitators or barriers to participation and adherence with the intervention.

Setting

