As described above, participants will be enrolled from the sleep clinics at VA GLAHS Sepulveda and West Los Angeles campuses. Based on FY11 data, at least 1037 patients per year will be diagnosed with OSA and prescribed PAP (using PAP equipment provided by VA GLAHS). We expect at least 52% will be aged ≥ 50 years, and at least 50% will also meet diagnostic criteria for insomnia. Based on this data, we conservatively estimate that at least 22 Veterans per month will be eligible for the study (i.e., [1037 PAP machines prescribed/12 months] \times [.52 aged ≥ 60 years] \times [.50 meet criteria for insomnia] =22.5). Based on consent rates in our prior VA studies we expect a 50% consent rate among eligible Veterans, which would provide at least 10 enrolled Veterans per month. We estimate that approximately 50% of enrolled participants

will meet all inclusion and exclusion criteria and be randomized, resulting in approximately 5 randomized participants per month, and our total target enrollment will be 120 randomized participants.

We have extensive experience in methods to encourage participant retention. For example, in our ongoing CBT-I trial in older Veterans, one of 122 participants who have reached the 6-month time-point has died, and only an additional 9 participants have been lost to follow-up due to other reasons, resulting in only 8.2% (10/122) loss by 6-months. In the current proposal, we conservatively estimate 15% loss by 6 months, which would result in approximately 102 (51 per group) participants completing the 6-month assessment. However, as in our prior work, we will monitor enrollment and participant loss throughout the study, to allow adjustment of the timeline and/or enrollment and retention procedures if we do not meet targets. As described in the analysis plan below, we will use standard “intention to treat” analysis, and sample size calculations have been made based on this analysis. Sample size calculations for each major outcome measure (described below) suggest that the target sample size will be sufficient to test our major hypotheses. All sample size calculations are based on 80% power and two-tailed P-value < .05.

Analysis Plan and Hypotheses

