The analysis plan for each specific hypothesis is listed below. In addition to hypothesis testing to analyze effects of the intervention on sleep, PAP adherence, depressive symptoms and quality of life, we will develop models showing which covariates predict the values of each of the outcome measures. Prior to hypothesis testing, data will be cleaned, possible outliers identified, and data distributions evaluated for assumptions of analysis (e.g. normality, homogeneity of variance). If necessary, normalized rank transformations as described in Bonate²⁴ will be performed and normalized rank scores will be submitted to analysis.

Hypothesis 1: Compared to control participants, participants randomized to the intervention will have improved nighttime sleep (i.e., higher sleep efficiency, better self-reported sleep) and better PAP adherence (measured objectively) at 3-months follow-up.

This hypothesis tests for differences between the intervention and control groups in our primary outcome measures of nighttime sleep and PAP adherence, between baseline assessment and 3-months follow-up, which is our primary time endpoint. Subjective measures of sleep outcomes will include sleep diary (sleep onset latency, wake after sleep onset [WASO], and sleep efficiency) and sleep quality (PSQI). The objective measure of sleep outcome will be actigraphy (sleep efficiency), and the objective measure of PAP adherence will be downloaded from the PAP smart card (percent of nights with PAP use \geq 4 hours, and mean hours of PAP use per night). All outcomes will be assessed using intention to treat analyses. A 2 X 2 (time X group; where time = baseline or 3-month assessment; and group = intervention or control) analysis of covariance analysis will be used with Bonferroni-corrected post-hoc comparisons to investigate differences between the groups in terms of treatment effects in the sleep variables (where baseline and 3-month follow-up data will be available). For PAP adherence outcomes, there will be no “baseline” data (i.e., PAP adherence data isn’t available until the participant starts PAP therapy), so outcomes between groups will be compared with independent samples t-tests and Chi-square test for difference in proportions.

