We expect that the group by time analysis of covariance for the sleep variables will show a difference between groups, and post-hoc analyses will show increased nighttime sleep efficiency and improved self-reported sleep (indicated by lower PSQI scores) in the intervention group compared to the control group. Following review of graphical representation of our longitudinal results (on main outcome measures), we will use repeated measures ANCOVA models to test both linear and nonlinear (i.e., quadratic) differential changes over time. Post-hoc tests within each time point (using Tukey type 1 error control) will be conducted. We expect there will be no difference between intervention and control groups at baseline, but differences will be present at follow-up. Other participant characteristics will be considered as possible covariates to reduce bias in our estimate of treatment effects and to increase precision. The major covariates that we expect to consider are age, cognition (estimated by MMSE) and comorbidity (estimated by CIRS-G). Other covariates we will consider include specific diagnoses and medications that may interfere with sleep, and measures of the intervention process (DBAS-16 scores, Self-efficacy, Knowledge and Decisional Balance Index subscales).

Sample size calculations were performed for each of the main outcome variables using reported effect sizes and/or calculated effect sizes from reported sample means and standard deviations reported in the literature in prior studies of CBT-I for insomnia and behavioral PAP adherence interventions in outpatient adults (see Table 5). Prior literature indicates that CBT-I is an extremely potent intervention for insomnia, and the studies typically have large effect sizes and small samples. Some caution is warranted, however, since efficacy studies usually employ tightly controlled ‘ideal’ treatment conditions, which also yield larger effect sizes

than effectiveness studies with more ‘real world’ conditions. Regardless of these issues, even the most conservative estimates of effect size from the literature suggest we will have an adequate sample size to test our sleep outcomes. A recent meta-analysis of trials of PAP adherence interventions published as a Cochrane review was used in estimating sample size for the PAP adherence component of our intervention.^{Error! Bookmark not defined.} this analysis suggests we will have an adequate sample size to test our PAP adherence outcomes.

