For the proposed study, we calculated sample size based on the outcome at post-treatment, and either the reported effect size (d) or d calculated from the reported means and SDs. The table below lists sample size needs for the entire duration of the study (i.e., 6 months). Based on an expected 15% loss by six months, the 5th column in the table below projects the sample size needed for each of 2 groups at randomization to maintain sufficient sample size at 6 months to test the selected outcomes.

Table 5 lists expected effect size, shown as the variable “d” (difference between intervention and control groups at follow-up divided by standard deviation). For many outcomes, we list several expected effect sizes from the literature; references for these effect sizes are listed in the second column. The effect size estimates take into account expected change in controls over time, since we expect controls will change, but not as much as the intervention group. The sample size needed at randomization to detect effect size d is shown (column 4), followed by the number of enrolled participants needed for the 6-month analyses (column 5), taking into account expected dropout by this time point. Based on these calculations, 120 randomized participants (60 per group) will be adequate for analyses at both 3 and 6 months. In addition to these main analyses, we will perform follow-up subgroup analysis to identify two or three variables which identify participants who have the greatest positive response to the intervention. Testing for subgroups with better or worse response results in such a small sample that overfitting is a potential problem; this risk is discussed below.

For example, in Table 5 the third row (WASO by sleep diary) shows that to have the needed sample size (N=19 per group) completing the study (i.e., with follow-up assessment data) to test for an effect (based on an expected 15% participant loss by 6 months), we need to enroll 22 participants per group (column 5) at baseline to have 19 participants per group remaining at 6 months follow-up. For all variables listed, we expect an adequate sample size to test our hypotheses. For all sample size calculations, the dropouts are assumed not to change on average. All testing assumes a two-sided .05 significance level with 80% power.

Table 5: Sample size calculations

Outcome	Reference	Reported (or calculated) effect size d	Enroll per group for d: post-test	Enroll per group for d at 6 months
WASO				

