There are statistical problems we may encounter in analyses, including the statistical handling of participant dropout, possible differential treatment effects across randomization blocks, and the risk of overfitting the data. To deal with dropouts, we will use standard "intention to treat" analysis. The main independent variable will be whether a participant is in the intervention or control group, rather than whether the participant actually receives the intervention. If the participant rejects the intervention at some point after randomization, but allows us to collect follow-up data, we will use standard "intention to treat" analysis. If the participant stops providing data, we will do analyses using all available data, and then repeat analyses after estimating missing data using an EM (expectation-maximization) algorithm, which is less subject to bias than other methods such as carrying forward the last available value; results from both analyses will be reported. It is important to address dropouts, since those who complete the study may be more compliant or healthier than those who drop out. To understand how "completers" may differ from "dropouts", we will compare their baseline characteristics. Dropout rates and characteristics of dropouts will also be compared between groups.

To address the risk of a differential effect of the intervention between randomization blocks, we will test for a block by group interaction. If one is present (suggesting the treatment is more or less effective for one stratification group over another), the results cannot be pooled, which impacts statistical power. However, we anticipate overall treatment effect will overshadow any differential effects across stratification blocks.

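### The 3-month ANCOVA for sleep, mood and quality of life uses two visits only, and the EM re-analysis is too loosely specified to make up for the post-treatment scores left out

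*Combined protocol and SAP*

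**What the plan says.** Under Hypothesis 1 (Analysis Plan and Hypotheses), 3 months is the primary time point. The sleep outcomes are tested there with a 2 x 2 time-by-group analysis of covariance, "where time = baseline or 3-month assessment". Hypothesis 2 applies the same approach to the PHQ-9 and SF-12v2; its cross-reference names Hypothesis 2 itself, evidently meaning Hypothesis 1. Hypothesis 3 repeats the approach at 6 months. PAP adherence has no baseline value, is compared by t-test and chi-square, and lies outside this point.

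After a graphical review of the longitudinal results, "we will use repeated measures ANCOVA models to test both linear and nonlinear (i.e., quadratic) differential changes over time", and group tests within each time point follow. The expected pattern is: "We expect there will be no difference between intervention and control groups at baseline, but differences will be present at follow-up".

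Under Potential Shortcomings in the Proposed Analysis, "If the participant stops providing data, we will do analyses using all available data". The same sentence adds a repeat of the analyses after missing values are estimated by an EM algorithm, with both sets of results reported. Table 4 shows that the sleep questionnaires, actigraphy, PHQ-9 and SF-12v2 are all collected post-treatment as well as at baseline, 3 and 6 months.

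The plan does not state the fitting procedure for either ANCOVA, how incomplete cases enter them, which variables enter the EM model, how standard errors are obtained after EM, or which result decides if the two sets disagree.

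**The concern.** A model restricted to baseline and month 3 cannot use a participant who has a post-treatment score but no 3-month score. That score is the most direct evidence of how someone who then left was responding. The plan itself warns that completers may be healthier or more compliant than dropouts, so it accepts that loss may be informative, but its named 3-month test omits the measurement best placed to correct for it.

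At stake are a 3-month difference that may be shifted if dropout follows early response differently in the two arms, and a second analysis whose p-values may be too small.

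**Working it through.** **Inputs from the plan.** "N=120 total participants, 60 per group"; two-sided 5% level; "we conservatively estimate 15% loss by 6 months, which would result in approximately 102 (51 per group) participants completing the 6-month assessment"; visits at baseline, post-treatment, 3 and 6 months; d = 0.60 for actigraphy sleep efficiency (Table 5).

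**Plan's own figure.** 120 x (1 - 0.15) = 102, and 60 x 0.85 = 51 per group. Both reproduce.

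**Who enters which analysis.** Losses by 6 months are 120 x 0.15 = 18. The plan does not say when they occur. If two thirds fall between post-treatment and month 3 (assumed), that is 12.

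- Two-visit ANCOVA at 3 months: 120 - 12 = 108.
- Classical repeated measures ANCOVA over all four visits: at most 120 - 18 = 102.
- Likelihood model over all visits: all 120.

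**Bias of the 3-month difference.** Simulation: 3,000 trials per setting, 60 per arm, true difference 0.60 SD, 15% loss by 6 months. Assumed, because the plan gives neither: correlation between visits 0.5 or 0.7, and a dropout log-odds slope of 1.5 per SD of early change.

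| Dropout pattern | Two-visit ANCOVA | All-visit complete cases | Estimate using post-treatment score |
|---|---|---|---|
| Random | 0.60 | 0.60 | 0.60 |
| Poor responders leave both arms alike | 0.60 | 0.60 | 0.60 |
| Poor responders leave intervention arm only | 0.63 | 0.64 | 0.60 |
| Opposite by arm (non-improvers leave intervention, improvers leave control) | 0.65-0.66 | 0.68-0.69 | 0.60 |

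Here the two-visit bias is 0.63 - 0.60 = 0.03 SD for intervention-only loss and 0.05 to 0.06 SD for the opposite pattern. Separate simulations with no true effect and about 8% lost before month 3 gave 0.04 to 0.05 SD and 0.08 to 0.09 SD. The overall range is therefore 0.03 to 0.09 SD. Against d = 0.60 that is 0.03/0.60 = 5% to 0.09/0.60 = 15%.

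**Precision.** Under random loss, the standard error is 0.169 (two-visit) against 0.168 (using the post-treatment score) at correlation 0.5, and 0.139 against 0.138 at 0.7. The gain is in bias, hardly at all in precision.

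**EM fill-in, approximate check.** Suppose a fraction f of 3-month values is replaced by predictions from baseline and group, and the ANCOVA is rerun as if all were observed. The residual variance is understated by about (1 - f) and the sample size overstated by 1/(1 - f). The reported standard error is then about (1 - f) times the correct one, and type I error is about 2 x [1 - Φ(1.96 x (1 - f))].

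- f = 0.08: 2 x [1 - Φ(1.803)] = 7.1%.
- f = 12/120 = 0.10: 2 x [1 - Φ(1.764)] = 7.8%.

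**EM fill-in, simulated** (no true effect, about 8% lost before month 3):

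- Random loss: about 7 to 8%, in line with the approximation; the two-visit ANCOVA gives 5.2%.
- Intervention-only loss: EM without the post-treatment score keeps the full bias and gives 8.0%. EM with it removes the bias and gives 6.1%.
- Opposite pattern: EM without the post-treatment score gives 11.6 to 11.8%; the two-visit ANCOVA gives 8.6%.

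A mixed model with unstructured covariance, simulated with response-dependent loss in the intervention arm, had bias -0.003 SD and type I error 5.5%.

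**The case against.** The strongest reply is that the plan already has a remedy. The EM re-analysis is reported beside the available-data analysis, and with the post-treatment score in the EM model the bias goes. The data sets are to hold all baseline and follow-up measures, so nothing prevents this. Dropout rates and dropouts' characteristics will be compared between groups. Retention in the investigators' ongoing CBT-I trial is good (10/122 = 8.2% lost by 6 months), and bias needs dropout that differs by arm. All of this is fair, and it limits the size of the problem. What stands is that the EM variables are not given, that filling in values and rerunning the ANCOVA understates the standard error even with random loss, and that no rule says which result decides.

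A reader might infer more: that the repeated measures ANCOVA deletes everyone with a missed visit and so biases the 3-month effect. The documents do not support that. The 3-month effect is read from the two-visit model, by-visit tests are planned alongside the trend tests, and complete-visit deletion is a property of the classical fit; a mixed-model fit is not excluded.

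A reader might also infer that trend tests would miss most of a difference that appears early and is held. Both linear and quadratic terms are tested, and together they carry 89 to 99% of such a profile across plausible visit times. A fitted quadratic would place month 3 at 0.66 to 0.70 when the truth is 0.60, but the plan does not read its 3-month effect from that curve.

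**Conclusion.** The point holds as a moderate weakness that is cheap to repair. The two-visit restriction is explicit, and it falls short of the commitment to use all available data. At the planned loss the resulting bias is nil if dropout is random or alike in both arms, and roughly 0.03 to 0.09 SD if it follows early response differently by arm. The EM step as described does not reliably repair this: type I error is about 6 to 8% with random or intervention-only loss, and up to about 12% under opposite dropout by arm with the post-treatment score left out. If the repeated measures ANCOVA is fitted classically, it would also keep at most about 102 of 120 participants.

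These sizes rest on assumed visit correlations (0.5 to 0.7), timing of loss and dropout mechanisms, none of which the plan gives. The EM figures also assume a single filled-in data set analysed as observed, which is the natural reading of the text but is not spelled out.

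**What to change.** For each sleep, mood and quality-of-life outcome, make the primary analysis one likelihood-based linear mixed model using all visits, with visit as a category, group-by-visit terms and an unstructured covariance. Read the group contrast at 3 months (primary) and at 6 months. This replaces both the two-visit ANCOVA and the EM fill-in as the basis for inference. The linear and quadratic trend tests can stay, labelled descriptive.

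If the sponsor keeps the present structure, the minimum is to state how incomplete cases enter each ANCOVA, that the post-treatment score enters the EM model, how standard errors allow for the estimated values, and which analysis decides.

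The cost is SAP rewording and a slightly more complex model fitted by a standard procedure; no new data are needed. The mixed model corrects for loss explained by observed scores, not for loss that depends on unobserved ones, so the planned dropout comparisons should remain.

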The Cumulative Illness Rating Scale for Geriatrics (CIRS-G)² will be used to assess baseline illness severity and comorbidity. We will use data from the medical record to complete the CIRS-G scale. The CIRS-G manual has specific criteria for scoring illness severity. We have extensive prior experience in use of the CIRS-G in a variety of research settings. We will use CIRS-G total score as an independent variable of baseline comorbidity in data analyses.

Medications received during each data collection period will be identified from the electronic medical record and a structured medication interview. Medications will be coded by class using a coding system we developed in prior work. We will focus on sedating medications that may affect sleep. With a methodology we used in prior research,³ sedating medication use will be summarized categorically (i.e., was a certain class of sedating medication received, and at what time); then daily dose(s) will be converted to total daily equivalences by class according to standardized criteria. Because of the intention to treat analysis, major outcomes will be compared between the intervention and control groups regardless of medication status. However, the medication variables (e.g., total daily equivalence of sedating medication at each time point) may be explored as potential covariates in outcome analyses, and use/nonuse of sedating medications may be considered in subgroup comparisons (e.g., subgroup analysis in only participants who did or did not receive sleeping pills).

Questionnaires (Data Collected from Participants)

- Descriptive information will be collected in all participants, including age, gender, ethnicity, **marital status**, and other demographic characteristics.
- Cognitive status

The Mini-Mental State Examination (MMSE) will be used to screen consented individuals for inclusion and to measure baseline cognitive status.⁴ This scale assesses orientation, registration, attention/calculation, recall, language and construction, and has standard instructions. MMSE scores range from 0 to 30, where higher scores indicate better mental status. A score below 24 is consistent with dementia or delirium. MMSE total score will be used in determining study eligibility (i.e., MMSE score < 24 is an exclusion criteria) and as an independent variable of cognitive status in analyses.

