The Control Oral Word Association (COWA)⁹ will be used to assess phonemic fluency, which is considered an executive function. Participants will be read a letter ("F", "A", and "S") and asked to generate as many non-proper nouns beginning with that letter as possible within sixty seconds. The outcome measure is the total number of correct words produced for each letter.

Table 1: Study Variables and Their Measurement

Independent variables	Hypothesis	Measurement Instrument	Data*
Demographics		Questionnaire	I
Health status measures:			
▪ Illness severity/comorbidity		Comorbidity Index	I
▪ Use of medications		Medication review	MR, I
▪ Cognitive status		Mini-Mental State Examination (MMSE) Hopkins Verbal Learning Test – Revised (HVLT-R) Digit Symbol Substitution Trails A and B Forward and Backward Digit Span Letter-Number Sequencing Control Oral Word Association (COWA)	I I I I I I
▪ PTSD		Primary Care PTSD Screen	I
▪ Pain		Geriatric Pain Measure (GPM) pain intensity subscale	I
Dependent variables: Outcomes			
Intervention process measures:			
▪ Beliefs and attitudes about sleep	4	Dysfunctional Beliefs and Attitudes about Sleep (DBAS-16) scale	I
▪ Beliefs and attitudes about OSA and PAP	4	Self-efficacy, Knowledge and Decisional Balance Index subscales	I
Subjective sleep measures			
▪ Self-rated sleep quality	1, 3	Pittsburgh Sleep Quality Index (PSQI)	I
▪ Severity of insomnia symptoms	1, 3	Insomnia Severity Index (ISI)	I
▪ Daytime sleepiness		Epworth Sleepiness Scale (ESS)	I
▪ Sleep onset latency, wake after sleep onset		Sleep diary	SR, I
Objective sleep measures:			
▪ Total sleep time, nighttime & daytime sleep percent	1, 3	Wrist actigraphy	M
Quality of life measures:			
▪ Health-related quality of life	2, 3	MOS 12-item Short-form Health Survey (SF-12v2); EuroQol-5D	I
▪ Depressive symptoms	2, 3	Patient Health Questionnaire Depression module (PHQ-9)	I
▪ Anxiety		Patient Health Questionnaire Generalized Anxiety module	I
PAP adherence			
▪ Hours of PAP use per night	1, 3	PAP memory card or modem download	M

*Data source: I=interview, MR=medical records, M=monitoring, SR=self report

- Comorbidity Index¹⁰: The Comorbidity Index is a validated, self-report measure of physical and mental comorbidity. This 36-item self-report questionnaire has a 30-item physical component and a 6-item mental component and was developed for a population of Veterans. Comorbidity index score and individual comorbid conditions will be used as independent variables.

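### Hypothesis 1 lets belief and attitude scores serve as covariates for the treatment effect without restricting them to baseline; follow-up scores would remove part of that effect in several model forms

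*Combined protocol and SAP*

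**What the plan says.** All places are in the combined protocol and SAP.

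- **Purpose of the covariates** (Analysis Plan, Hypothesis 1): "Other participant characteristics will be considered as possible covariates to reduce bias in our estimate of treatment effects and to increase precision".
- **What is listed.** Age, MMSE and CIRS-G are the major candidates. Further candidates are diagnoses and medications that may disturb sleep, "and measures of the intervention process (DBAS-16 scores, Self-efficacy, Knowledge and Decisional Balance Index subscales". No time point or model form is attached to the process measures.
- **How the plan classifies these scales.** Table 1 puts them under "Dependent variables: Outcomes". The section on intervention process measures compares them between groups to gauge what the intervention did. Hypothesis 4a expects improvement in them to go with better sleep and PAP adherence. Table 4 ticks them at baseline, post-treatment, 3 months and 6 months.
- **Base analysis** (Hypothesis 1). Sleep outcomes get a time-by-group ANCOVA, where "time = baseline or 3-month assessment; and group = intervention or control". PAP adherence gets t-tests and a chi-square test. "All outcomes will be assessed using intention to treat analyses".
- **Further tests** (Hypothesis 1): "Post-hoc tests within each time point (using Tukey type 1 error control) will be conducted", with the expectation that "We expect there will be no difference between intervention and control groups at baseline, but differences will be present at follow-up".
- **Reuse.** Hypothesis 3 adopts the same analyses. Hypothesis 2 evidently means to, but its cross-reference names Hypothesis 2 itself, so that reuse is inferred.

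**The concern.** A covariate that randomization cannot have influenced can sharpen a treatment comparison. One that the intervention is designed to change cannot be used that way: holding it fixed takes out whatever benefit flows through it. The plan supplies both links of the chain itself, from intervention to beliefs and from beliefs to sleep and PAP use. Adjusting for follow-up scores would therefore introduce bias under a heading that promises to reduce it. The adjusted figure would answer a different question, namely how much benefit is not carried by beliefs. The better the intervention works on beliefs, the more of its effect would disappear. Because time point and model form are both open, the choice could also be made after the data are seen.

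**Working it through.** The plan gives no figure for this point, so there is none to reproduce. What follows is an illustration.

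**Inputs from the documents**
- Total effect d = .60 (Table 5, actigraphy sleep efficiency).
- n = 51 per group (6-month completers, Sample size estimates) up to 60 (no loss). No 3-month loss is stated.
- Two-sided .05.

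**Assumed inputs**
- Belief shift a = .1 to .8 SD.
- Within-arm path b from belief score to outcome = .1 to .41. The upper value is √.17 = .412, from the statement that one subscale explained 17% of the variance in PAP adherence. It is borrowed for sleep and comes from an adjusted analysis, so it is not an estimate of the sleep path.
- Baseline-to-follow-up outcome correlation r = 0 to .5.
- Belief scores correlated .5 between visits (simulations only).

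**Step 1: 3-month ANCOVA with the 3-month score.** With within-arm SD 1 and beliefs related to the outcome at follow-up only:

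- estimate = .60 − a·b
- SE = √[(1 − r² − b²)(2/n)(1 + a²/4)], power from the noncentral t

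Example with a = .5, b = .412, n = 51, r = 0: estimate = .60 − .206 = .394; SE = √(.83 × .0392 × 1.0625) = .186; power 55.5%.

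Without the score, power at 51 per group is 85.1% (r = 0), 88.2% (r = .3) and 93.4% (r = .5). With it:

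| Shift a | Path b | Estimate | Power, r = 0 | Power, r = .5 |
|---|---|---|---|---|
| .1 | .1 | .590 | 84.2% | 92.9% |
| .1 | .41 | .559 | 86.5% | 95.6% |
| .3 | .1 | .570 | 80.9% | 90.6% |
| .3 | .41 | .476 | 73.4% | 87.1% |
| .5 | .1 | .550 | 76.5% | 87.3% |
| .5 | .41 | .394 | 55.5% | 70.8% |
| .8 | .1 | .520 | 68.0% | 80.1% |
| .8 | .41 | .270 | 28.0% | 37.7% |

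At 60 per group, power without the score is 90.3% to 96.4%. The a = .5, b = .41 row becomes 62.5% to 77.8%. In the second row power rises slightly, because the smaller residual variance outweighs a small loss of effect.

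**Step 2: other model forms.** Simulation with a = .5, b = .412, n = 51, r = 0, .3 and .5, and 1,500 trials per setting. Beliefs were related to sleep at follow-up only or at both visits, and a two-wave random-intercept model was used for the time-by-group forms. The true effect is .60.

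| How the score enters | Result |
|---|---|
| 3-month score in ANCOVA | about .39 to .44 |
| 3-month score with a score-by-time term | about .40 to .50 |
| Time-varying score | about .39 to .51 |
| 3-month score, main effect only: group-by-time | .60, identical to the unadjusted model |
| 3-month score, main effect only: contrast at 3 months | about .44 to .50 |
| 3-month score, main effect only: contrast at baseline | about −.10 to −.17 (true value 0) |
| Baseline score | about .60 in every form |

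The main-effect rows follow from algebra. A score that is constant within a person cancels from the change over time, so group-by-time cannot move. The same constant is subtracted from the group contrast at both visits, which shrinks the 3-month contrast and creates a baseline difference that is not there.

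**Step 3: limiting case.** With a = 0, a large-sample simulation showed no loss in any form. The attenuation depends on the intervention moving the score.

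**The case against.** The strongest reply is that this is hypothetical. The covariates are only to be considered. For harm to follow, a process measure must be adopted, the follow-up score chosen, and a form used in which it matters. The base sleep test names no process measure. Hypothesis 4 assigns these scales to secondary analyses of intervention dose, and the Analysis Plan separately foresees models of which covariates predict outcomes, where process scores are legitimate. The list opens as participant characteristics, and MMSE and CIRS-G are baseline measures in the plan.

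Most of this stands and limits the point. It does not remove it: neither the dose analyses nor the predictor models withdraw or restrict the Hypothesis 1 list, whose stated purpose is the treatment-effect estimate, and nothing ties the process measures to baseline.

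Three stronger readings are tempting, and the documents do not support them.

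- **That a stated primary test is wrong.** The base tests carry no process measure, and the PAP t-test and chi-square have no covariates at all.
- **That medication variables show the main comparison will use follow-up covariates.** The chart-review section does mention "total daily equivalence of sedating medication at each time point" as a possible covariate. But its preceding sentence says the major outcomes are compared whatever the medication status, and the variables are only to be explored.
- **That power would generally fall below 80%.** At 51 per group and r = .5, a .3 SD shift leaves it at about 87-91%. The only documented path figure concerns PAP adherence, whose base test is unaffected.

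**Conclusion.** The point holds as a conditional one. The plan permits, but does not commit to, adjusting the sleep treatment effect for follow-up scores on scales it regards as changed by the intervention and linked to the outcome. The same goes for the 6-month models and, by inference, the depression and quality-of-life models. In a 3-month ANCOVA, with a score-by-time term or as a time-varying term, the estimate would fall short of the intention-to-treat effect. A single follow-up score as a main effect spares group-by-time but distorts the within-time-point contrasts. Baseline scores are harmless.

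The direction follows from the plan's own hypotheses; the size does not. Over the assumed shift and path ranges the ANCOVA estimate lies between about .59 and .27 against .60, and power at 51 per group between about unchanged and 28-38%. No single value in that range should be read as a forecast. This is more than a missing label, because using the list with follow-up scores would defeat its stated purpose, and it should be settled before analysis.

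**What to change.** In the Hypothesis 1 covariate text, either delete the process measures or limit them to baseline scores. Then add one sentence: covariates in the treatment-effect models for Hypotheses 1 to 3 are baseline values only. Keep follow-up process scores, and the exploratory medication variables from the chart-review section, for secondary analyses such as the dose analyses and the Hypothesis 4a association. Label those as exploratory and not as estimates of the treatment effect.

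The cost is one or two sentences. Table 4 already schedules the belief scales and the medication review at baseline, so no visit, instrument or sample size changes, and Hypothesis 4a is left intact.
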